7.3 Safety

The safety population includes all randomized subjects who receive at least 1 dose of study medication. The safety population will be analyzed as treated and will be used for the safety analyses. No data will be excluded for any reason.

8. General Statistical Considerations

8.1 Unit of Analysis

The unit of analysis in this study will be the study eye for all ocular efficacy and safety summaries and the subject for all non-ocular summaries.

8.2 Missing or Inconclusive Data Handling

Partial/missing start and end dates for AEs and concomitant medications will be imputed as follows:

Partial/missing start date:

- Dates with missing day only will be imputed as the 1st of the month unless the month and year are same as the month and year of first dose of study medication, in which case missing day will be imputed as the first dose day of study medication.
- Dates with both day and month missing will be imputed as 1 Jan unless the year is same as the year of first dose of study medication, in which case missing day and month will be imputed as the first dose day and month of study medication.
- Completely missing dates will be imputed as the first dose date of study medication unless the end
 date is on or before the first dose date of study medication, in which case missing date will be
 imputed as 1 Jan of the same year as the end date.

Partial/missing end date:

- Dates with missing day only will be imputed as the last day of the month unless the month and year
 are the same as the month and year of the last dose of study medication, in which case missing
 day will be imputed as the last dose day of study medication.
- Dates with both day and month missing will be imputed as 31 Dec unless the year is same as the
 year of the last dose of study medication, in which case missing day and month will be imputed as
 the last dose day and month of study medication.

- If the ongoing flag is missing or "Yes" then the date will not be imputed unless death date is available, in which case the missing date will be imputed as the death date. If ongoing is "No" then the missing end date will be imputed as the last dose date.
- If the imputed date is after the date of death, then the end date will be set equal to the date of death.

The original dates will be displayed in data listings and the imputed dates will be used in derivations only (study day, treatment-emergence status, etc.).

The strategy for handling intercurrent events from Section 2.5 will be utilized for imputing missing data during the primary analyses of the primary efficacy variables.

8.3 Definition of Baseline

Baseline is defined as the last measurement prior to the first dose of study medication. Change from baseline will be calculated as, Follow-up Visit – Baseline Visit.

8.4 Data Analysis Conventions

All data analyses will be performed by SDC after the study is completed and the database has been locked and released for unmasking, as described in Section 6.2. Statistical programming and analyses will be performed using SAS® Version 9.4 or higher. Output will be provided in rich text format (RTF) for tables and portable document format (PDF) for tables, listings, and figures using landscape orientation.

Summaries for continuous and ordinal variables will include the number of observations (n), arithmetic mean, standard deviation (SD), median, minimum, and maximum. Minima and maxima will be reported with the same precision as the raw values; means and medians will be presented to one additional decimal place than reported in the raw values. Standard deviations will be presented to two additional decimal places than reported in the raw values.

Summaries for discrete variables will include counts and percentages. All percentages will be rounded to one decimal place (i.e., XX.X%). Differences between active treatment groups and placebo (vehicle) will be calculated as active minus placebo (vehicle) and change from baseline will be calculated as follow-up visit minus baseline.

All statistical tests will be two-sided with a significance level of 0.05 (α = 0.05) unless otherwise specified. Confidence intervals (CI) for differences between treatment groups will be two-sided at 95% confidence. All p-values will be rounded to 4 decimal places; p-values less than 0.0001 will be presented as "<0.0001"; p-values greater than 0.9999 will be presented as ">0.9999."

Unless otherwise specified, tabular summaries will be presented by treatment group and, where appropriate, visit. Listings will be based on all randomized subjects, unless specified otherwise, and sorted by subject number, visit, and parameter as applicable.

9. Disposition of Subjects

Subject disposition will be presented in terms of the numbers of subjects who were screened, screen failures, and randomized, by treatment group and overall for all screened subjects. The numbers and percentages of subjects who were included in the FAS, Per-Protocol, and Safety analysis populations as well as who completed the study and discontinued from the study will be presented by treatment group and overall for all randomized subjects. Subjects who are not discontinued from the study will be considered study completers. The reasons for discontinuation will be summarized by treatment group and overall for all discontinued subjects. Percentages will be calculated using discontinued subjects as the denominator. The reasons for study discontinuation that will be summarized include: adverse event (AE), lost to follow-up, protocol violation, study terminated by sponsor, withdrawal by subject, lack of efficacy, and other. The number and percentage of subjects with any deviation, major deviation, and minor deviation will be summarized by treatment group and overall for all randomized subjects.

The reasons for screen failure (i.e., subject did not meet eligibility criteria) will be displayed with the percentages calculated using total number of screen failures as the denominator.

Details of the study randomization, including study site, randomization date, randomized treatment, and actual treatment, will be provided within a subject listing.

A subject listing for subject disposition will include study completion or discontinuation date, study completion status, and the primary reason for study discontinuation (if applicable).

For protocol deviations, a subject listing will be provided that includes the date of the deviation, visit at which the deviation occurred, the deviation category, the deviation description, if the deviation was related to COVID-19, and the classification of whether the deviation was judged to be major or minor in a masked review prior to database lock.

A subject listing of inclusion/exclusion criteria will include whether if all eligibility criteria were met, the specific eligibility criterion which was not met (if applicable), and the visit at which the eligibility criterion was not met (if applicable).

A subject listing of analysis population inclusion will include whether criteria were met for inclusion in the FAS, Per-Protocol population, and Safety population.

10. Demographic and Pretreatment Variables

10.1 Demographic Variables

The demographic variables collected in this study include age, gender, ethnicity, race, and iris color. Subjects who record more than one race will be grouped into a single category denoted as multi-racial. Iris color will be summarized at the eye level. Demographic variables will be summarized for the FAS.

Age (years) will be summarized, overall and by treatment, using continuous descriptive statistics. Age will also be categorized as follows: < 65 years and ≥ 65 years.

The number and percentage of subjects will be presented, overall and by treatment, for age category, gender, ethnicity, race, iris color, and study site.

A subject listing that includes all demographic variables will be provided.

11. Medical History and Concomitant Medications

11.1 Medical History

Medical history will be coded using the Medical Dictionary for Regulatory Activities (MedDRA) Version 25.0.

Ocular medical history will be summarized using discrete summary statistics and presented by treatment group and overall separately for study eyes and fellow eyes by System Organ Class (SOC) and Preferred Term (PT) using the Safety population. Non-ocular medical history will be similarly summarized at the subject level. If a subject reports the same PT multiple times within the same SOC, that PT will only be reported once within that SOC. As with the PT, if a subject reports multiple conditions within the same SOC, that SOC will only be reported once. In the summaries, SOCs will be sorted in alphabetical order, and PTs within an SOC will be sorted in order of descending frequency across all subjects.

Listings of medical history will be generated separately for ocular and non-ocular data.

11.2 Concomitant Medications

Concomitant medications will be coded using World Health Organization Drug Dictionary (WHODrug) Global B3 01Mar2022 and summarized to the therapeutic drug class (Anatomical Therapeutic Chemical [ATC] 4 classification) and preferred name. If the ATC 4 classification is not provided, then the next highest classification that is provided in the coding dictionary will be used. The preferred name will be defined as the active ingredient; if the active ingredient is not provided or includes more than two ingredients (e.g., multivitamins), then the drug name will be summarized as the preferred name.

Prior medications are defined as those medications with an end date before the date of initiation of study drug administration. Concomitant medications are defined as those medications listed as having been taken (1) prior to initiation of study drug administration and continuing for any period of time following the first administration of study drug or (2) at any time following the first administration of study drug.

Concomitant medications will be summarized using the FAS. Medications will be tabulated for each treatment group using frequencies and percentages. Subjects may have more than one medication per

ATC text. At each level of subject summarization, a subject will be counted once if they report one or more medications. Percentages will be based on the number of subjects in each treatment group. In the summaries, ATC classes and preferred names within an ATC class will be sorted in alphabetical order.

All medications utilized for lowering IOP or for rescue will be noted in the subject listing of prior and concomitant medications. IOP-lowering medications and rescue medications are each a subset of medications where the investigator has indicated on the eCRF that the medication was used to lower IOP or rescue. Rescue medications and criteria are described in Section 4.3.

The number and percentage of subjects initiating IOP-lowering medications will be presented by treatment group for each post-baseline visit as well as across all post-baseline visits for the Safety population.

Listings of prior and concomitant medications will be generated separately for ocular and non-ocular data. A separate listing will be generated for IOP-lowering medications.

11.3 IOP-Lowering Procedures

All IOP-lowering procedures will be coded using MedDRA Version 25.0 and presented in a subject listing.

12. Dosing Compliance and Treatment Exposure

12.1 Dosing Compliance

Details of individual administrations of study medication done at home by subjects are not captured within the clinical database, therefore dosing compliance will not be summarized.

12.2 Treatment Exposure

The number and percent of subjects receiving at least one dose of study medication (i.e., Safety population) will be summarized as part of subject disposition.

Although not captured directly on the eCRF, additional variables related to study drug administration will also be derived for summarization:

- Study drug interruption (yes/no), where interruptions will be identified via presence of a TEAE
 where action taken with study drug was marked as "drug interrupted" or a protocol deviation
 indicating study drug was interrupted.
- Premature discontinuation of study drug (yes/no), where discontinuations will be identified via presence of a TEAE where action taken with study drug was marked as "drug withdrawn" or a protocol deviation indicating study drug was prematurely discontinued. Subjects who discontinue the study prior to Visit 6 () will also be reviewed to verify if study drug was prematurely discontinued or not.
- Study drug completion, defined as those subjects where premature discontinuation of study drug is not equal to "yes".

A masked data review will be conducted prior to database lock and unmasking to identify any other cases of study drug interruption or premature discontinuation of study drug which are known to have occurred,

but are not identified through the criteria above. The classifications from this final review will be used for analysis.

The number and percentage of subjects with study drug interruption, premature discontinuation of study drug, and study drug completion will be presented by treatment group.

Subject data listings will be generated to present details of study drug assignment, study drug replacement, as well as first instillation of study medication performed in-clinic on Visit 2 Details about study drug accountability will also be listed.

13. Efficacy Analyses

Sections 13.1.1 to 13.1.5 describe the sensitivity analyses for the handling of intercurrent events to be performed for the primary efficacy variables.

13.1.1 SENSITIVITY ANALYSIS I

The handling of intercurrent events will be updated as follows:

- Receipt of rescue medication: observed data for visits after receipt of rescue medication will be singly imputed as failure [hypothetical strategy].
- Missing data for any reason: missing data will be multiply imputed from the placebo (vehicle) treatment arm assuming missingness not at random [hypothetical strategy].

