## Sensitivity Analysis I

The hypothetical strategy will be used for the intercurrent event. All missing data will be imputed assuming missing not at random (imputing from the vehicle treatment arm). The following SAS code will be used to generate the multiple imputation datasets:

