13.1.2 SENSITIVITY ANALYSIS II

The intercurrent event will be updated as follows:

- Receipt of rescue medication: observed data for visits after receipt of rescue medication will be singly imputed as failure [hypothetical strategy].
- Missing data for any reason: missing data will be multiply imputed using randomized treatmentbased MCMC methodology [hypothetical strategy].

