13.1.5 SENSITIVITY ANALYSIS V

The handling of intercurrent events will be updated as follows:

- Receipt of rescue medication: observed data for visits after receipt of rescue medication will be singly imputed as failure [hypothetical strategy].
- Missing data for any reason: missing data will be singly imputed as failure [hypothetical strategy].

Treatment comparisons will be made using Pearson's chi-squared test. If any of the expected cell counts are less than five, an exact 95% CI for the difference in proportions and Fisher's exact test will be used instead.

	-		
I			
Ī			
I			

14. Safety Analyses

All safety analyses will be conducted using the Safety population.

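### Sensitivity Analyses I and II count a rescued eye as a failure only if the later visit is observed; a rescued subject who misses the visit goes to multiple imputation and can be scored a responder

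*SAP*

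**What the plan says.** SAP 13.1.1 and 13.1.2 each replace the base handling of intercurrent events with two rules.

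- **Rescue, both analyses:** "observed data for visits after receipt of rescue medication will be singly imputed as failure". The rule is limited to data that were observed.
- **Missing data, Sensitivity Analysis I:** "Missing data for any reason: missing data will be multiply imputed from the placebo (vehicle) treatment arm assuming missingness not at random".
- **Missing data, Sensitivity Analysis II:** again whatever the reason, "missing data will be multiply imputed using randomized treatmentbased MCMC methodology".

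Neither section says which rule takes precedence for a subject who is both rescued and missing, and neither exempts rescued subjects from imputation. Both rules carry the label of a hypothetical strategy. The protocol's descriptions of the same two analyses (section 11.6.1) also send all missing data to imputation and contain no exemption.

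Sensitivity Analysis V (SAP 13.1.5) has the same rescue rule but a different second rule: "Missing data for any reason: missing data will be singly imputed as failure".

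Protocol 6.6 and 9.6.2 keep rescued subjects enrolled and attending. Section 6.6 adds that they enter the sensitivity analyses. SAP 8.2 refers to SAP Section 2.5 for the intercurrent-event strategy of the primary analyses; that section is not in the public text.

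**The concern.** In these analyses rescue overrides even a favourable observation: a rescued eye with a cell grade of 0 at Visit 6 is still a failure. Protocol 3.4.1 ties rescue to Grade 2 or greater cells or severe pain. Nothing visible explains why such an eye should regain a chance of success because the subject did not attend. As written, outcome after rescue depends on attendance.

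Two things are at stake. First, the estimates in I and II may be shifted by subjects whose outcome the plan otherwise regards as settled. Second, the comparison among sensitivity analyses is blurred. Going from I or II to V should show only the effect of the missing-data assumption for unrescued subjects. Here it also changes the outcome of rescued subjects who miss the visit. The same gap applies to pain at Visit 4 for anyone rescued before that visit.

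**Working it through.** **Step 1. Apply the rules to two subjects.** Suppose both are rescued on Day 6.

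| Subject | Visit 6 cell score | Sensitivity I | Sensitivity II | Sensitivity V |
|---|---|---|---|---|
| A | observed | failure | failure | failure |
| B | missing | imputed from vehicle | imputed from own arm | failure |

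B is a responder in some share of the imputed datasets and A in none. The two differ only in attendance.

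**Step 2. Inputs.** The planned size is 120 per arm (protocol synopsis). The public text gives no rescue rate, missing-visit rate or response rate, so there is no plan figure to reproduce and the rest is assumed: 30 vehicle and 10 OCS-01 subjects rescued before Visit 6, and 10 to 30% of them without a Visit 6 score.

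**Step 3. Formula.** Added response in an arm = (number rescued × share missing × imputed success probability) / 120. If every post-rescue visit were a failure, this term would be zero in both arms.

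**Step 4. Sensitivity I.** Imputation is from vehicle, so one probability serves both arms; take 20 to 40%.

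- Vehicle: 30 × 0.1 × 0.2 / 120 = 0.5 points, up to 30 × 0.3 × 0.4 / 120 = 3.0 points.
- OCS-01: 10 × 0.1 × 0.2 / 120 = 0.17 points, up to 10 × 0.3 × 0.4 / 120 = 1.0 point.
- The difference shrinks by 0.33 to 2.0 points.

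**Step 5. Sensitivity II.** Imputation is by randomized arm, so the probabilities differ.

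- At 25% vehicle and 55% OCS-01, vehicle gains 30 × 0.1 × 0.25 / 120 = 0.63 to 30 × 0.3 × 0.25 / 120 = 1.88 points. OCS-01 gains 10 × 0.1 × 0.55 / 120 = 0.46 to 10 × 0.3 × 0.55 / 120 = 1.38 points. The difference shrinks by 0.17 to 0.50 points.
- At 20% and 60%, both arms gain the same amount (30 × 0.2 = 10 × 0.6 = 6), so the net change is zero.

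**Step 6. Direction.** If rescued-and-missing subjects occur only on OCS-01, the shift favours OCS-01. For 1 to 6 such subjects it is 1 × 0.15 / 120 = 0.12 to 6 × 0.30 / 120 = 1.5 points in I (vehicle probability 15 to 30%). In II it is 1 × 0.35 / 120 = 0.29 to 6 × 0.60 / 120 = 3.0 points (OCS-01 probability 35 to 60%).

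**Step 7. Wider grid.** Take rescue of 10% vehicle and 3% OCS-01 up to 50% and 20%, 2 to 20% of the rescued missing the visit, and response of 15% versus 35% up to 30% versus 60%. The difference then changes by −0.01 to −1.80 points. Power for a two-sided 0.05 test of two proportions with 120 per arm falls by at most 2.6 points. That largest fall is from 0.952 at 15% versus 35% to 0.926 at 16.5% versus 35.6%, the rates after adding 0.50 × 0.20 × 0.15 = 1.5 points to vehicle and 0.20 × 0.20 × 0.15 = 0.6 points to OCS-01.

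**The case against.** The best defence is that the public text is incomplete. SAP Section 2.5, the rescue section (4.3) and the imputation code announced in the protocol are not visible, and any of them could set rescue to failure before imputation starts. This limits certainty but does not remove the point: 13.1.1 and 13.1.2 say they update the base handling, and their own wording sets no order.

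It can also be said that the hypothetical label supports imputing after rescue. But the same label sits on the rule that makes observed post-rescue data failures, so it does not tell a programmer which treatment a missing post-rescue visit should get.

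The argument on size largely stands. Rescued subjects are meant to keep attending, so 30% missing is a generous upper limit, although subjects may withdraw at any time and SAP section 9 lists lack of efficacy as a reason for leaving the study. If the imputation model conditions on earlier visits already set to failure, the success probability would be lower, though not zero. So such a subject can become a responder, not will. Study success rests on the primary test, and V already gives an analysis without the gap.

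A reader might go further and infer that the primary result carries the same flaw, or that I and II quietly alter the responder definition. The documents support neither. Both inferences need the primary rule, which is not in the public text, and the two rules in 13.1.1 and 13.1.2 are stated openly.

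**Conclusion.** As written, SAP 13.1.1 and 13.1.2 give an inconsistent result for rescued subjects: failure if seen, possible responder if not. This is a defect in a stated rule, confined as far as can be seen to two sensitivity analyses.

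Under the assumed 30 and 10 rescued subjects with 10 to 30% missing, the difference shrinks by about 0.3 to 2.0 points in Sensitivity I and about 0 to 0.5 points in Sensitivity II. A reader might infer that the error always works against OCS-01. That does not follow: in II it can cancel, and in either analysis it would favour OCS-01 if rescued-and-missing subjects were concentrated there. The effect is probably small and unlikely to decide the trial's conclusion, but it makes I and II harder to interpret and leaves room for two programmers to produce different results.

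**What to change.** In SAP 13.1.1 and 13.1.2, state that all visits after receipt of rescue medication, whether observed or missing, are analysed as failure, and that multiple imputation applies only to missing visits of subjects not rescued before that visit. Check that Section 2.5 and the imputation code follow the same order, rescue first and imputation second.

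The cost is one sentence in each section and one programming condition. SAP 11.2 already has rescue medication flagged on the eCRF, and SAP 8.2 already covers partial start dates for concomitant medications. No new data are needed, and the change should be made before unmasking.

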13.1.2 SENSITIVITY ANALYSIS II

The intercurrent event will be updated as follows:

- Receipt of rescue medication: observed data for visits after receipt of rescue medication will be singly imputed as failure [hypothetical strategy].
- Missing data for any reason: missing data will be multiply imputed using randomized treatmentbased MCMC methodology [hypothetical strategy].

13.1.3 SENSITIVITY ANALYSIS III

The primary efficacy analysis will be performed using the PP population with observed data only. Treatment comparisons will be made using Pearson's chi-squared test. If any of the expected cell counts are less than five, an exact 95% CI for the difference in proportions and Fisher's exact test will be used instead.

